Subsequently, thanks also to the new scientific assumptions offered by the discovery of mirror neurons, attempts were made to apply MT also in post-stroke neurorehabilitation, both for upper limb motor recovery and for the treatment of spatial neglect (19-25).The studies conducted so far have yielded interesting results, however only a few works have been performed with a significant number of participants and with appropriate experimental designs. Among the most important works, Yavuzer and colleagues (21) completed a study on 40 post-stroke patients in the subacute phase (within 12 months after stroke), reporting a better recovery on upper limb function in patients treated with MT compared to untreated patients. In another randomized trial involving 36 patients, Dhole and colleagues (19) showed that even in the post-acute phase (starting from 6 weeks after stroke), MT seemed to induce a greater recovery of upper limb function in patients with severe hemiparesis. In this study, no effects of MT on spatial neglect, nor an impact of the presence of spatial neglect on motor recovery using MT were found. However, according to Ramachadran and colleagues (20) and to our working group (21), spatial neglect can have an impact on the ability to observe a body image reflected into a mirror and, consequently, on the correct execution of a MT protocol.

In conclusion, although the results obtained so far using MT are encouraging, an optimal MT protocol for patients with hemiparesis, who can present or not spatial neglect, is not available. Furthermore, although there are many evidences regarding the efficacy of starting neurorehabilitation immediately after a cerebral accident, no studies on MT have been performed in the early post-acute phase.

Aim

The aim of the present study is to demonstrate the efficacy of MT in a selected group of patients and to propose an optimal protocol for treatment specifically designed for this clinical population. Thanks to a targeted recruitment and to the accurate control of various clinical-instrumental variables that can play a decisive role in the effectiveness of a rehabilitative therapy, it will be possible to demonstrate the efficacy of MT in the functional recovery of the hemiplegic patient. The primary objective focuses on the motor recovery of the upper limb. We also propose as a secondary objective to demonstrate that MT can promote a global functional improvement of the patient in daily living activities.

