Materials and methods

Trial design

Single-blind, randomized controlled trial with the aim of evaluating the effect of MT, added to a standard neurorehabilitation protocol, in a selected population of post-acute patients.

Participants

We will consecutively recruite all post-stroke patients admitted to our neurorehabilitation clinic.

Inclusion criteria are as follows:

- Ischemic/hemorrhagic stroke, which determines hemiparesis or hemiplegia.
- Time post onset no longer than 4 weeks
- Age between 18 and 80 years.
- First stroke or stroke recurrence without previous functionally evident motor outcomes.
- MMSE (Mini Mental State Examination) ≥ 24 (29-30)
- Absence of global aphasia. Comprehension deficit, when present, should be minimal, mild or moderate (Token Test score, Aachener Aphasie Test < 40) (33-34)
- Spatial neglect (can be present or not)
- Ideomotor apraxia (can be present or not)
- No other pathologies (e.g., upper limb joint-muscle) that could interfere with motor recovery
- No other seriously invalidating clinical conditions (cardiopathies, bronco pneumopathies)

The recruitment will take place according to the following specifications: during the daily clinical briefing of each Operative Unit of our Centre, physicians inform the physiotherapist coordinators about the patients admitted for post-stroke hemiparesis and coordinators, in turn, inform the physician and the physiotherapists responsible for the study.

1- Clinical Screening

The Medical Specialist in charge of the project will: (i) verify that the patients accomplish with the clinical and neuroimaging inclusion criteria in order to access the study; (ii) obtain the informed consent signed;

(iii) fill in the registration form and (iv) refer the patient to the neuropsychologist responsible for the project.

2- Neuropsychological screening with integrated cognitive evaluation

The neuropsychologist will perform a deep cognitive evaluation investigating: global cognitive functioning (Mini Mental State Examination) (29-30); presence of aphasia (Token Test, Aachener Aphasie Test, 33-34; oral naming, Batteria per l'Analisi dei Deficit Afasici, 35); spatial neglect (line and bell cancellation, 31-32; , 38; complex figure copy 39, 40; clock drawing test, 40; test for personal neglect, 41); ideomotor apraxia (movement imitation test, 36), and mood disorders (Hamilton Depression Rating Scale, 37). Patients will be randomly assigned to the MT or control group (CT).

Interventions

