- FIM (Functional Independent Measure): 18-voice scale that analyses different activities of daily life. The score in each item varies from 1 (complete dependence) to 7 (complete self-sufficiency), thus offering a cumulative score and a score profile in the various items. In this way the degree of self-sufficiency in performing elementary functional activities such as personal care, sphincter control, mobility, locomotion (motor area) and communication and social interaction (cognitive area) is measured. The administration of this scale will take about 10 minutes.

The primary outcome consists in the motor recovery of the upper limb, evaluated using the Fugl-Meyer scale (27). Secondary outcome are a specific physiatrist scale for the upper limb, the Action Research Arm Test (ARAT, 28), and a generic functional scale, the Functional Independent Measure (FIM, 26).

Sample size and randomization

Data analysis will be performed by a biostatistics, blind with respect to the treatments performed. The sample size will be constituted of 40 patients (randomized in 20 for the experimental group, MT, and 20 for the control group, CT).

Randomization will be performed according to the block randomization procedure, which allows to balance the quantitative asymmetry of the patients assigned to the two groups. The "block" is a sequence of the randomization list, which contains the same number of patients to be assigned to patients treated with MT and to controls (CT). For example, a block of 4 generates six different sequences, each of which assigns two patients to the MT group and two to the CT: MT-MT-CT-CT, MT-CT-MT-CT, CT-CT-MT, CT-MT-CT-MT, MT-CT-CT-MT, CT-MT-MT-CT. Thanks to the progressive balanced assignment, block randomization guarantees a similar number of patients enrolled in the two groups.

Statistical analysis

It was calculated to have a power of 0.80 and to demonstrate an effect size of .90 (difference between the two treatments equal to 90% of the variability of the phenomenon) to a Student t test for independent data, performed at a significance level of 0.05 (two-tailed test).

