Considering that the model of the analysis of covariance (ANCOVA), used for inferential analysis, has a greater expected efficiency (less residual variability) of at least 30%, it can be considered that the aforementioned sample size will allow to highlight also an effect size of around 0.7. The variables will be described by mean, median, standard deviation (quantitative variables) and absolute frequency and relative percentage (qualitative variables). Furthermore, for the differences between before and after treatment for the variables detected for each group, the 95% confidence intervals will be calculated. The analysis of the main and secondary variables will be carried out by analyzing the covariance (satisfied assumptions) with the base value as a covariate, the treatment group as a factor and inserting the variables relevant to the response to the treatment, which presented an unsatisfactory balance between the two groups at baseline. The effectiveness of the therapeutic intervention will be reported also in terms of effect size (difference between the variations of the scores in each group in relation to the total variance).

Expected results

The functional outcomes of stroke and the pathophysiological characteristics of the patients affected can be extremely variable. The standardization of patient groups is an extremely delicate moment in the design of efficacy studies of rehabilitation treatments. We believe that in this study a scrupulous standardization of the sample, the process of randomization, the separation of information between those responsible for patient assessment and data processing and analysis, may be the appropriate approach for the study of a correctly selected and homogeneous population.

Indeed, MT presents the scientific and physiological assumptions to positively impact on the patient's functional recovery with post-acute early-onset stroke. However, in order to highlight this aspect, it is necessary that the treatment is designed in strict relation with the patient's characteristics and that possible biases and interfering factors are carefully controlled.

Hopefully, with the careful execution of the proposed study design, it will be possible to demonstrate the efficacy of MT in the functional recovery process of the paretic upper limb of hemiplegic patients. This effective results will be expressed through the score improvement of the specific scales employed in the study.

Bibliography

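### Randomisation is not stratified by spatial neglect, although the protocol says neglect can affect mirror therapy and tests it before allocation; stratifying would be a cheap improvement

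*Combined protocol and SAP*

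**What the plan says.** - **Introduction.** Citing other researchers and the protocol's own working group, it says that "spatial neglect can have an impact on the ability to observe a body image reflected into a mirror", and hence on whether MT is performed correctly. It also reports that a cited randomised trial of 36 patients found no impact of neglect on motor recovery with MT. It concludes that "an optimal MT protocol for patients with hemiparesis, who can present or not spatial neglect, is not available".
- **Participants, inclusion criteria.** Both kinds of patient are eligible: "Spatial neglect (can be present or not".
- **Participants, neuropsychological screening.** Neglect is assessed with several tests, including line and bell cancellation. Random assignment is described at the end of this step.
- **Sample size and randomization.** "The sample size will be constituted of 40 patients (randomized in 20 for the experimental group, MT, and 20 for the control group, CT"). On method: "Randomization will be performed according to the block randomization procedure, which allows to balance the quantitative asymmetry of the patients assigned to the two groups". A block of 4 is given as an example. No stratification factor is stated.
- **Statistical analysis.** The ANCOVA has the baseline score as covariate and treatment group as factor. Variables relevant to treatment response are added if they turn out poorly balanced at baseline. Neglect is not named, no threshold is given, and no comparison by neglect status is planned.

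**The concern.** The protocol raises neglect as something that may alter how MT is delivered, measures it in everyone before allocation, and then makes no use of the measurement when allocating. Blocking on numbers keeps the arms equal in size and does nothing for their composition. With 20 patients per arm, a moderate chance difference in neglect is not rare.

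Two things are at stake. If neglect is related to motor outcome, an imbalance adds noise to the treatment comparison, and a reader of a 40-patient result will wonder how much of it is case mix. And because adjustment depends on a judgement made after baseline data are seen, whether neglect enters the primary model is left open, when it could be settled beforehand.

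**Working it through.** **1. The plan's own figure.** Inputs from Statistical analysis: "It was calculated to have a power of 0.80 and to demonstrate an effect size of .90", and "performed at a significance level of 0.05 (two-tailed test"). The normal approximation gives n per arm = 2(1.960 + 0.842)² / 0.90² = 19.4, so 20 per arm and 40 in total, as stated. The exact t calculation needs 20.39 (21 per arm), and power at 20 per arm is 0.792. The stated size reproduces, and nothing below changes it.

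**2. Chance imbalance in neglect, fixed count.** The documents give no prevalence; 25-40% is assumed, that is 10 to 16 of 40. With K neglect patients and a 20/20 split, the number X in the MT arm is hypergeometric: P(X = x) = C(K, x)·C(40−K, 20−x) / C(40, 20). The difference between arms is |2X − K|.

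For K = 10, a difference of 4 or more means X ≤ 3 or X ≥ 7: 2 × (0.0002 + 0.0040 + 0.0282 + 0.1043) = 0.273.

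| K | P(4 or more) | P(6 or more) |
|---|---|---|
| 10 | 0.273 | 0.065 |
| 11 | 0.155 | 0.031 |
| 12 | 0.301 | 0.082 |
| 13 | 0.176 | 0.041 |
| 14 | 0.320 | 0.096 |
| 15 | 0.191 | 0.048 |
| 16 | 0.333 | 0.105 |

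The values alternate because an even K allows only even differences and an odd K only odd ones, so for odd K the first column really means 5 or more. The fixed-count ranges are 15.5-33% and 3-10.5%.

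**3. Count left random.** The count is not known in advance, so this is the better summary. Simulating unstratified blocks of 4 (200,000 runs), with each patient independently having neglect:

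| Assumed prevalence | P(4 or more) | P(6 or more) |
|---|---|---|
| 25% | 0.198 | 0.042 |
| 30% | 0.224 | 0.056 |
| 40% | 0.257 | 0.075 |

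That is about 20-26% for a gap of at least 4/20 = 20 percentage points, and about 4-8% for at least 6/20 = 30 points.

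**4. Possible effect on the estimate.** Assume neglect shifts the outcome by g SD, with g between 0.5 and 1.0 (not in the documents). A gap of t patients moves the unadjusted standardised difference by g·t/20. For t = 4 that is 0.10 to 0.20; for t = 6 it is 0.15 to 0.30. For scale, the target is 0.90 and the standard error of the difference is √(2/20) = 0.32 SD.

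**5. With stratified blocks of 4.** Complete blocks balance exactly. Only the last block in a stratum can be incomplete, leaving at most 2 patients' difference. Two strata can leave total arm sizes at most 2 + 2 = 4 apart, that is 22/18. Simulation (20,000 runs at each prevalence from 20% to 50%) gave the same maxima.

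**6. What stratifying does not buy.** Detectable difference within the neglect stratum at 80% power, two-sided 0.05:

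| Neglect patients | Equal split | Split 4 apart |
|---|---|---|
| 10 | 2.02 SD (5/5) | 2.21 SD (3/7) |
| 12 | 1.80 SD (6/6) | 1.90 SD (4/8) |
| 16 | 1.51 SD (8/8) | 1.56 SD (6/10) |

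Balance improves this by only about 3-8%, because the number of neglect patients is unchanged.

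**The case against.** The strongest reply is that unstratified blocking with a baseline-adjusted ANCOVA is an acceptable design, and that the plan already has a route to adjust for neglect if it is imbalanced. Chance imbalance under valid randomisation does not bias the test in expectation. A 4-patient gap would move the unadjusted estimate by less than one standard error even on the larger assumed effect. Evidence on neglect is mixed by the protocol's own account. Ideomotor apraxia is admitted on the same terms, and 40 patients support few strata, so choosing neglect is partly a preference.

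Most of this stands, and it limits the point to a cheap improvement. It does not remove it. The adjustment clause leaves both the variable and the trigger to a judgement made after baseline data are seen. Neglect, unlike apraxia, is the characteristic the Introduction singles out as able to affect MT.

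A reader might infer more than the documents support:

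- *That neglect prevents MT, or is the foundation of the rationale.* The text says only that it can have an impact. The rationale rests on the mirror neuron system and early treatment, and the stated objectives are upper-limb recovery and daily activities.
- *That stratifying would show whether MT works in neglect patients.* Step 6 of the working shows it would not.
- *That neglect drives exits under the attention rule.* The protocol draws no such link; it says only that records of inattentive patients will be considered when analysing factors affecting MT efficacy.

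**Conclusion.** The point holds as a cheap improvement and is not a flaw that invalidates the trial. Neglect is raised by the protocol as relevant to MT, known before allocation, and left unbalanced by the randomisation. Adjustment for it is conditional and unspecified.

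On an assumed prevalence of 25-40%, a gap of 4 or more neglect patients would arise in about one trial in four or five (20-26%), and a gap of 6 or more in about 4-8%. The cost is precision and ease of interpretation. The 0.10 to 0.20 SD shift for a 4-patient gap rests on a further assumption about how strongly neglect predicts outcome. Block size 4 is the protocol's example and not a stated commitment, and dropout was not modelled.

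**What to change.** 1. Define neglect as present or absent by one fixed rule from tests already in the screening battery, for example a pathological result on line or bell cancellation, written down before the first patient is randomised.
2. Prepare two block lists, one per stratum.
3. Include neglect as a prespecified factor in the primary ANCOVA, whatever the observed balance.
4. If the MT minus CT difference is shown by neglect status, label it descriptive only.

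The cost is one extra list, one definition and one degree of freedom. Arm totals may end slightly off 20/20 (at worst 22/18 with blocks of 4). No test, visit or patient is added. Stratification does not address exits after randomisation under the attention rule, which need separate handling in the analysis plan.

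### Does the claim that ANCOVA lets 40 patients detect an effect size of around 0.7 overstate what the trial can show?

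*Combined protocol and SAP*

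**What the plan says.** Under Sample size and randomization in the combined protocol and SAP: "The sample size will be constituted of 40 patients", 20 per arm. The Statistical analysis section gives the basis: "It was calculated to have a power of 0.80 and to demonstrate an effect size of .90", using a two-sided Student t test at the 0.05 level. It explains the 0.90 as a "difference between the two treatments equal to 90% of the variability of the phenomenon".

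The next sentence turns to the analysis that will actually be used, an ANCOVA "with the base value as a covariate, the treatment group as a factor", plus any relevant variables that are poorly balanced at baseline. The model, it says, "has a greater expected efficiency (less residual variability) of at least 30%, it can be considered that the aforementioned sample size" and this sample "will allow to highlight also an effect size of around 0.7". No baseline-to-T1 correlation and no source for the 30% are given.

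The same section later describes the effect size to be reported as the "difference between the variations of the scores in each group in relation to the total variance".

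**The concern.** Efficiency of one analysis relative to another is ordinarily a ratio of variances. Read that way, a 30% gain shrinks the detectable effect only by the square root of the gain, and 0.90 falls to about 0.75 to 0.79, not 0.7. The later reference to total variance could be taken to support that reading.

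The 0.7 is also the only sensitivity figure offered for the planned primary analysis, since the t test serves only to size the trial. If it were too favourable, a reader of a null result would credit the trial with a 20% chance of missing an effect of 0.7 when the chance was 27% to 31%.

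**Working it through.** **Inputs.** From the plan: n = 20 per arm, two-sided alpha 0.05, power 0.80, effect size d = 0.90, ANCOVA gain 30%. Assumed: no losses, and baseline as the only covariate (residual df = 40 − 3 = 37).

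**1. Reproduce the base design.** By normal approximation, n per arm = 2(1.960 + 0.842)²/0.90² = 15.70/0.81 = 19.4, rounded up to 20. Power at 20 per arm is 81.2%, and the detectable effect is 2.802 × √(2/20) = 0.886. The exact noncentral t (df 38) gives 79.2% power and a detectable effect of 0.909; 21 per arm would be needed to pass 80%. The plan's 20 per arm is reproduced by the approximation.

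**2. Apply the 30%.** Let f be the residual SD after adjustment divided by the unadjusted SD. The noncentrality is (d/f) × √(n/2). Simple scaling gives a detectable effect of 0.90f; the normal approximation gives 0.886f.

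| Reading of 30% | f | 0.90f | Detectable, exact | Detectable, normal | Power at 0.7, exact | Power at 0.7, normal |
|---|---|---|---|---|---|---|
| Relative efficiency 1.3 (variance/1.3) | 0.877 | 0.79 | 0.798 | 0.777 | 69.1% | 71.4% |
| Variance × 0.7 | 0.837 | 0.75 | 0.761 | 0.741 | 73.1% | 75.4% |
| SD/1.3 | 0.769 | 0.69 | 0.700 | 0.681 | 80.0% | 82.1% |
| SD × 0.7 | 0.700 | 0.63 | 0.637 | 0.620 | 86.8% | 88.5% |

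Simulated ANCOVAs gave power at 0.7 of 68.6%, 71.8% and 85.9% for the first, second and fourth rows, close to the exact values. Without adjustment, power at 0.7 is 57.8%.

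**3. What 0.7 requires.** Exact 80% power at 0.7 needs f = 0.769, so f² = 0.592: a variance cut of 40.8%, or an SD cut of 23.1%. By normal approximation f² = 0.624, a variance cut of 37.6%. The plan gives 30% as a minimum, so a gain of that size on the variance scale is not excluded.

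**4. Which scale the wording supports.** A standardised difference of 0.90 is a share of the SD, so variability in the t-test sentence means the SD. The ANCOVA sentence follows directly and explains efficiency in parentheses with the same word. Read consistently, 0.90/1.3 = 0.69, which is the printed figure. The total-variance phrase is weak evidence the other way: a difference in means is not normally standardised by a variance, so the phrase suggests loose vocabulary.

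**5. Why a correlation cannot simply be supplied.** If the effect size is in SDs of the T1 score, f² = 1 − r², so f² = 0.70 needs r = 0.55 and f² = 0.592 needs r = 0.64. If it is in SDs of the change score, with equal variances at T0 and T1, f² = (1 + r)/2, so the same values need r = 0.40 and r = 0.18. The required correlation falls in one case and rises in the other as the gain grows. The plan's description of effect size by score variations points towards change scores but does not settle it.

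**The case for a change.** The strongest opposing case is that a stated minimum supports only what the minimum delivers. On the usual meaning of efficiency, that is 0.76 to 0.80, nearer 0.8 than 0.7, with a power shortfall at 0.7 of 7 to 11 points. If the SD scale was meant, the 30% stands for a variance cut of 41% (SD/1.3) or 51% (SD × 0.7), more than a reader would take from the words, and it has no source. Exits for low attention and extra covariates could lower power a little further.

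Part of this stands. The scale, the standardising SD and the basis for 30% are not written down, and on the variance scale the shortfall at exactly 0.7 is real at the minimum gain. What does not follow is that the printed figure is wrong. The authors explain efficiency in their own words, and that explanation, read with the preceding sentence, returns their number. The size of the shortfall also depends on method: under the normal approximation, which gives the plan's 20 per arm, a 30% variance cut yields a detectable effect of 0.74 and 75% power at 0.7. The plan claims no more than an approximate figure.

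**Conclusion.** The concern does not call for a change. The documents do not show an arithmetic error: on the SD scale the stated figure is reproduced (0.69 by simple scaling, 0.700 exactly at 80% power). On the variance scale, with a gain of exactly 30%, the detectable effect would be about 0.76 to 0.80 and power at 0.7 about 69% to 73% (0.74 to 0.78 and 71% to 75% by normal approximation). These figures assume 20 analysed per arm and baseline as the only covariate.

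What remains is missing detail in a secondary remark. The 40 patients rest on the effect size of 0.90, which reproduces, and the ANCOVA, its baseline covariate and the significance level are the same under every reading. After the trial, what the data can rule out is judged from the confidence interval for the treatment difference, not from this planning sentence. Rewriting it around a particular correlation would add an assumption the plan does not make, and one that changes with the SD used.

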trial, unless there will be a clear trend of improvement in attention levels in the last sessions. Records of patients that will not show a sufficient level of sustained attention during therapy will be consider in the analysis of possible factors that affect the efficacy of MT rehabilitation. The mirror intervention both for the study group and for the control group will be in add-on modality and standard rehabilitation activity will be regularly plan.

Outcome measures

Functional evaluation

Four physiotherapists, after performing a joint training of 2 months, will deal alternatively and on randomized assignment with the functional assessment or treatment. Therefore, the physiotherapist who deals with the treatment will not be the same that will evaluate the patient both at T0 (baseline) and at T1 (after treatment).

The functional evaluation performed at T0 and T1 will be based on the following scales, which will constitute the outcome measures.

- Fugl-Meyer Asessment (FMA): a specific complex scale for stroke. In our study, we will use a part of the scale, specifically the 33 items used to evaluate motor function, coordination, somatic sensitivity and excursion of the joints of the upper limb (27). The administration of the scale will involve the execution of gestures with increasing complexity, pure or finalized engines. The score is based on the direct observation of the patient's performance in relation to the latter's ability to complete the item (score 2), to partially execute it (score 1), not to do it at all (score 0). The final score is given by the sum of the scores of all the items (from 0 to 66). The administration of the scale takes 35-40 minutes.

- Action Research Arm Test (ARAT): scale for the study of the functionality of the upper limb. It consists of 19 items grouped into 4 subtests (28). The items allow analysing both simple and finalized motor acts with variable difficulty. The score is based on the direct observation of the patient's performance: from the ability to complete the task on time (score 3), to the possibility of completing the task in a longer time than expected (score 2), to perform the task in an incomplete way (score 1), up to the total impossibility to complete the task (score 0). The score can therefore be between 57 and 0. The administration of the scale takes 10 minutes.

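### The ARAT analysis fixes only T0 ARAT as a covariate; T0 Fugl-Meyer, measured in everyone, enters only on chance imbalance, which may cost precision if many patients start at ARAT 0

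*Combined protocol and SAP*

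**What the plan says.** The Statistical analysis section applies a single model to FMA (primary) and to ARAT and FIM (secondary): an analysis of covariance "with the base value as a covariate, the treatment group as a factor". Read naturally, the base value is each outcome's own T0 score. The same sentence adds, conditionally, factors thought to bear on treatment response on which the arms prove poorly matched at baseline. It gives no threshold for a poor match.

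Under Outcome measures, ARAT has 19 items scored 0 to 3 (total 0 to 57). The item scale runs "up to the total impossibility to complete the task (score 0"), and an incomplete attempt earns 1. FMA has 33 items scored 0 to 2 (total 0 to 66). As described there, it covers motor function, coordination, sensation and joint range of the arm. Both scales are taken at T0 and T1.

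Under Participants, the first criterion is "Ischemic/hemorrhagic stroke, which determines hemiparesis or hemiplegia", with onset at most 4 weeks before. No minimum arm function or ARAT score is listed.

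**The concern.** A patient who cannot perform any of the 19 ARAT tasks, even in part, totals 0. All such patients share one T0 value, so within that group T0 ARAT carries no information about who will recover. Hemiplegia early after stroke is admitted, and the Introduction motivates mirror therapy by the difficulty of treating severe deficits, so scores of 0 are possible by design.

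T0 FMA measures the same limb in the same patients and may still rank those whom ARAT ties at 0. Whether the ARAT model uses it depends on chance imbalance between two arms of 20. If the arms happen to match on FMA, it stays out however prognostic it is. At stake is the width of the ARAT interval, together with one covariate choice that is left until the data are seen.

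**Working it through.** **1. The plan's own figure.** Inputs from Statistical analysis and from Sample size and randomization: "It was calculated to have a power of 0.80", "to demonstrate an effect size of .90", "to a Student t test for independent data", "performed at a significance level of 0.05 (two-tailed test"), and "randomized in 20 for the experimental group, MT, and 20 for the control group, CT".

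n per arm = 2(1.960 + 0.842)² / 0.90² = 15.70 / 0.81 = 19.4, so 20. This reproduces the stated 40. Exact noncentral-t power at 20 per arm is 79.2%.

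The plan expects ANCOVA to cut residual variability by at least 30%. That gives a detectable effect of 0.90 × √0.70 = 0.75 if the 30% is variance, or 0.90 × 0.70 = 0.63 if it is SD. The plan's figure of around 0.7 lies between. Nothing in this step uses ARAT.

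**2. Cost and break-even of a second covariate at N = 40.** With q covariates, the variance of the group effect is inflated by 1 + q/(N − q − 3).

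- q = 1: 1 + 1/36 = 1.0278
- q = 2: 1 + 2/35 = 1.0571
- Ratio: 1.0571 / 1.0278 = 1.0286

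Let r be the partial correlation of T0 FMA with T1 ARAT, given T0 ARAT. Then the variance ratio is (1 − r²) × 1.0286. Break-even: r² = 1 − 1/1.0286 = 0.0278, so r = 0.17.

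| r (assumed) | Variance ratio | Change in SE | Equivalent N (40 / ratio) |
|---|---|---|---|
| 0 | 1.029 | +1.4% | 39 |
| 0.3 | 0.936 | −3.3% | 43 |
| 0.4 | 0.864 | −7.0% | 46 |
| 0.5 | 0.771 | −12.2% | 52 |
| 0.6 | 0.658 | −18.9% | 61 |

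**3. Dependence on the share at ARAT 0.** The documents give no value for this share, so it is varied by simulation with 20 per arm. All inputs are assumed: severity SD 15 points; mean gain 12; FMA noise SD 3, 6 or 9; recovery SD 8, 12 or 18; FMA lying 5 or 20 points above ARAT. The last column is a separate simulation of the same trial size, also on assumed inputs; its limits are within 0.01 of the first.

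| Share at T0 ARAT 0 | Variance ratio, with / without T0 FMA | Middle inputs (noise 6, recovery SD 12): offset 20; offset 5 | Separate simulation |
|---|---|---|---|
| 24% | 0.84 to 1.02 | 0.98; 1.00 | 0.85 to 1.03 |
| 50% | 0.74 to 1.01 | 0.92; 0.98 | 0.73 to 1.01 |
| 66% | 0.67 to 1.00 | 0.88; 0.96 | 0.67 to 1.00 |

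The last column, as percentage change in variance, is +3% to −15%, +1% to −27%, and 0% to −33%. The limits shift with modelling details such as noise on ARAT itself, so they show the scale of the effect and are not estimates for this trial.

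**4. Cross-check with a different model.** This one is set in correlations, again assumed: latent T0–T1 correlation 0.6 to 0.9; FMA with severity 0.8 to 0.9; ARAT with severity 0.95; FMA floor share one quarter, and T1 ARAT floor share one half, of the T0 ARAT floor share.

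| Share at T0 ARAT 0 | Change in SE from adding T0 FMA |
|---|---|
| none | +1.0% to −3.0% |
| 20% | +0.7% to −4.9% |
| 40% | +0.3% to −7.6% |
| 60% | −0.7% to −11.8% |
| 80% | −2.5% to −18.9% |

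In the case with correlations 0.75 and 0.9, R² from T0 ARAT alone falls from 0.51 with no floor to 0.30 with 80% at 0. Adding T0 FMA at 80% raises R² from 0.297 to 0.434, and power for a 0.7 SD effect from 72% to 80%. At 60% at 0, R² rises from 0.395 to 0.468 and power from 78% to 82%.

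**The case against.** Adjusting each outcome for its own baseline is standard and defensible. Several stronger readings are tempting, and the documents do not support them.

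- **That T0 FMA goes unused.** It is the fixed covariate of the primary model, and the imbalance clause can bring it into the ARAT model. What stands is that entry there is not guaranteed and does not turn on prognostic value.
- **That everyone with a severely weak arm scores 0.** Incomplete performance of a single task already scores 1. Only complete inability on all 19 items gives 0, and the documents do not say how many such patients to expect.
- **That T0 FMA will separate the patients at 0.** FMA items also score 0 when not done at all, and ARAT also gives partial credit. FMA covers additional domains and so may separate these patients, but the documents do not show that it does.
- **That the adjustment fails.** T0 ARAT still divides patients at 0 from those above and ranks the latter. In the cross-check it explains 30% of the variance even with 80% at 0.

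No gain, or a slight loss, is compatible with the documents. That objection stands in full against any single figure for lost precision. It does not stand against the change itself, because the possible loss is small and bounded while the possible gain is much larger.

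**Conclusion.** The point holds as a low-cost improvement in efficiency, not as the correction of an error. The text fixes only T0 ARAT for the ARAT model and leaves T0 FMA to chance imbalance. The size is unknown, because it rests on two quantities that the documents do not give: the share of patients at ARAT 0, and the partial correlation of T0 FMA with T1 ARAT. With few patients at 0 the change is close to nil in most settings. It becomes material with a large share at 0 (about 60% or more) or a strong T0–T1 correlation.

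A reader might infer that the ARAT comparison is biased or the trial undersized. Neither follows: randomisation protects the comparison under either model, the primary FMA analysis already carries T0 FMA, and the sample size was not derived from ARAT. Importance is minor, and confidence in a real gain is low.

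**What to change.** State in the Statistical analysis section, before any outcome data are seen, that the ARAT ANCOVA includes T0 ARAT and T0 FMA as covariates and treatment group as factor, whatever the observed balance. The FMA model keeps T0 FMA as it is.

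The cost is one phrase of text and one residual degree of freedom (36 instead of 37), with no new data. The change also removes one covariate decision that would otherwise depend on the observed baseline.
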